Sanofi Pasteur	Split virion BP	Inactivated	> 6 months	<50
MSD	Intanza	Inactivated	> 18 years	<24
Astra Zeneca	FLUENZ	Live attenuated	2 – 18 years	<240

Table 1: Ovalbumin content in influenza vaccines available in UK. Green book chapter 19: 207-209 (accessible at <http://immunisation.dh.gov.uk/category/the-green-book>)

A trivalent Live Attenuated Intranasal Vaccine (LAIV), given via the intranasal route, has been available in the United States for several years (8). It has demonstrated efficacy against influenza in children from 2-17 years old (9-12). LAIV is also grown in hens’ eggs and contains ovalbumin.

The safety of trivalent LAIV in non-egg-allergic children has been established predominantly in the MI-CP111 trial (13). Table 2 depicts the safety data collected during the first 10 days post vaccination. In this study, all children received both an intranasal spray and an intramuscular injection. The nasal placebo dose (saline) was associated with significant nasal symptoms (parent/subject reported) but on day 0-1 the incidence of this was considerably lower at only 12%. The quadrivalent vaccine has been found to have a similar safety profile [REF].

	Injection Site Reaction	Runny Nose/ Nasal Congestion	Fever >100°F	Fever >101°F	Fever >102°F
TIV n=4232	25%	46%	12%	7%	4%
LAIV n=4243	21%	57%	15%	8%	4%
	p <0.001	p <0.001	p <0.001	NS	NS

Table 2: Percentage of children with adverse events on days 0-10 after immunisation with LAIV from Study MI-CP111 (13)

LAIV is contraindicated in children under 2 years old. This is because there has been increased incidence of wheezing in children under 2 years old in the 4 weeks following immunisation (13, 14). This effect is not seen in older children (13, 15, 16), even in those with pre-existing asthma and wheeze (17). Post marketing surveillance data has not reproduced this signal (18). LAIV is not associated with new onset asthma (16).

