NB: See Summary of Product Characteristics for full details of contra-indications to LAIV. Note that **Fluenz is not recommended during pregnancy. Administration of another live vaccine (e.g. MMR) within the previous 4 weeks is no longer a contra-indication to LAIV administration, according to updated DoH guidelines.**

Children requiring oral steroids for their asthma management (ie. BTS Step 5) may be included in the study if they meet the following criteria:

1. Their asthma is stable on their current regimen and has been so for the previous 2 weeks
2. They are reviewed by the centre PI prior to inclusion in the study
3. Their Asthma Control Test score at inclusion is no lower than 20.

SUBJECT WITHDRAWAL

The primary outcome in this study involves a single visit to a hospital for administration of the intranasal vaccine. Subsequent withdrawal will affect only the assessment of delayed symptoms, a secondary outcome measure, which will be collected by telephone.

TRIAL CLOSURE

The study will be considered complete following enrolment of the last patient and completion of the study procedures in that patient, or at the end of the influenza season 2014-15. Upon review by the ISC, recruitment may be extended if target recruitment is achieved prior to end of the influenza season and additional funding is available.

[figure not shown]
The study will be placed on hold and, upon review of study data and discussion with the IDMC, may be terminated early if any of the following occur:

- One patient suffers an allergic reaction that warrants admission to the ICU and use of mechanical ventilation
- Death of a participant during the study period, from any cause
- Two similar SUSARs (Suspected Unexpected Serious Adverse Reactions) or the repetition of one SUSAR

A teleconference will be scheduled within 72 hours if any of the aforementioned situations occur. This conference will be attended by the members of the IDMC and the ISC. At this teleconference the clinical relevance of the findings will be determined and recommendations may be made by the IDMC which may include:

- requesting further information
- modifying the protocol
- stopping enrolment
- institute more frequent monitoring guidelines
- termination of study

STUDY VISITS, PROCEDURES SCHEDULE and Patient Flow Diagram

	Visit 1	Phone follow up at 72 hours	Follow-up (by phone or email) after 4 weeks
Written Informed Consent (parent/ guardian)	X		
Written assent (child)	X		
Medical assessment	X		

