Any allergic reaction happening during the observation period following vaccine administration will be managed according to local policy. For the purpose of this protocol, we would suggest that mild (non-anaphylactic) symptoms should be treated with a long-acting, non-sedating oral antihistamine such as cetirizine (at doses listed in cBNF). Symptoms of anaphylaxis will be treated according to UK Resuscitation Council guidelines (reproduced below).

ADVERSE EVENT REPORTING

DEFINITIONS

An **adverse event** is any occurrence or worsening of an undesirable or unintended sign, symptom, laboratory finding, or disease that occurs during participation, including occurrences that are not necessarily caused by or related to the administration of the medicinal product under investigation. An adverse event will be followed until it resolves or until 30 days after a participant terminates from the study, whichever comes first.

A **serious adverse event (SAE)** is defined as any adverse event that suggests a significant hazard. This includes but is not limited to any of the following:

1. Death: Any death that occurs during the study must be reported whether considered treatment related or not.
2. A life-threatening event: Any adverse therapy experience that, in the view of the investigator, places the participant at immediate risk of death from the reaction as it occurred.
3. Inpatient hospitalization or prolongation of existing hospitalization.
4. Persistent or significant disability.
5. An event that requires intervention to prevent permanent impairment or damage. An important medical event that may not result in death, be life threatening, or require hospitalization may be considered an SAE when, based on appropriate medical judgment, it may jeopardize the participant and may require medical or surgical intervention to prevent one of the outcomes listed above.

An **adverse reaction** is a AE attributable to the medicinal product under investigation, in this case the Fluenz vaccine. If the adverse reaction meets the above criteria (1-6) then it is termed a **Serious Adverse Reaction (SAR)**. Where the SAR is considered 'unexpected' i.e. its nature or severity is not consistent with the investigator's protocol, these events will be termed **serious unexpected severe adverse reactions (SUSARS)**.

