The adverse event or reaction can be described as 'expected' if it caused symptoms and/or signs that could be reasonably described as a consequence of an allergic reaction or following vaccination. Symptoms of an allergic reaction are defined as any described within this protocol, or those in the view of the investigator that are an expected consequence of vaccination.

Any symptoms requiring treatment for anaphylaxis (adrenaline, steroids, salbutamol) will be classified as a SERIOUS ADVERSE REACTION and must be documented on both the CRF as well as through completion of a SAE form. The local investigator should also make a notification to the MHRA should also be made through the yellow card scheme (<https://yellowcard.mhra.gov.uk/>).

For the purpose of this study, SARs and SAEs will only be collected where onset is within 72 hours of vaccine administration.

DOCUMENTATION OF ADVERSE EVENTS

Safety data will be recorded on a specifically designed case report form (CRF). All serious adverse events (SAEs) or reactions (SARs) will be reported on an SAE report in addition to CRFs. Safety data will be reviewed after three months by the Independent Data Monitoring Committee (IDMC). The IDMC has the authority to recommend termination of the trial because of safety findings.

Throughout the study, the investigator will record all adverse events on the appropriate CRF regardless of their severity or relation to study medication or study procedure. The investigator will treat participants experiencing adverse events appropriately and observe them at suitable intervals until their symptoms resolve or their status stabilizes. SAEs will be recorded on the SAE report form and reported to the ISC within 24 hours. SARs will also be reported to MHRA through the yellow card system.

GRADING AND ATTRIBUTION OF ADVERSE EVENTS

NON-ALLERGIC REACTIONS

The study site will grade the severity of adverse events experienced by study participants according to the criteria set forth in the NCI-CTCAE Version 3.0

(http://ctep.cancer.gov/protocolDevelopment/electronic_applications/docs/ctcae3.pdf).

This document provides a common language to describe levels of severity, to analyse and interpret data, and to articulate the clinical significance of all adverse events.

Adverse events will be graded on a scale from 1 to 5 according to the following standards in the NCI-CTCAE manual:

Grade 1 = mild adverse event.

Grade 2 = moderate adverse event.

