APPENDIX 3: TOPIC GUIDE FOR TELEPHONE FOLLOW-UP AT 4 WEEKS

**** For patients with asthma/recurrent wheeze only ****

Participants' families will be contacted by the local research team between 4-5 weeks after LAIV administration, to determine whether their child has experienced any change in their lower respiratory symptoms which might be attributable to the vaccine. This telephone consultation will take approximately 2-3 minutes. If after three attempts (on three separate days) the local study team is unable to contact the family, the child will be deemed lost to follow up.

Guide to telephone interview:

1. Confirm interviewee's identity
2. Introduce yourself:

"I am <name> from the SNIFFLE-2 Study. Your child <participant's name> had the 'flu vaccine with us one month ago, and we arranged to speak to find out if you had needed to do anything different with his asthma/wheezing"
3. Complete appropriate Asthma Control Questionnaire over the telephone

(see separate questionnaires)
4. Finally, ask the following questions:
 - i) *Since the vaccine, have you had to take <participant's name> to see a Doctor because of his/her breathing?*
 - ii) *(If YES) – did you have to take them to hospital?*
 - iii) *(If YES) – did <participant's name> have to stay in hospital overnight?*

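### The 72-hour limit on collecting serious events has no exception for deaths or SUSARs, which other sections treat as study-wide, and it leaves later hospital stays without an SAE route

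*Protocol*

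**What the plan says.** The limit closes the Definitions section of Adverse Event Reporting: "For the purpose of this study, SARs and SAEs will only be collected where onset is within 72 hours of vaccine administration".

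Other provisions reach further:

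- Item 1 of the SAE definition, in the same section: "Any death that occurs during the study must be reported whether considered treatment related or not".
- Item 3 of that definition: "Inpatient hospitalization or prolongation of existing hospitalization".
- Trial Closure lists among its hold triggers "Death of a participant during the study period, from any cause" and "Two similar SUSARs (Suspected Unexpected Serious Adverse Reactions) or the repetition of one SUSAR".
- Serious Adverse Event Reporting has the coordination centre notify the MHRA, the ethics committee and the sponsor of all SUSARs in the study, with no onset limit.
- On the duration of follow-up, Definitions says: "An adverse event will be followed until it resolves or until 30 days after a participant terminates from the study, whichever comes first".
- Documentation of Adverse Events has investigators record all adverse events on the CRF throughout the study. SAEs also go on an SAE form and to the ISC within 24 hours. Serious Adverse Event Reporting then passes them to the IDMC chair, the ISC chair and the sponsor.

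Two contacts can bring later events to light. The 72-hour call may be made up to day 7 (Telephone Follow Up Visit, Appendix 2). The contact for children with asthma or recurrent wheeze takes place at 4-5 weeks, and the telephone guide in Appendix 3 asks whether the child did "have to stay in hospital overnight" since the vaccine. The section on asthma control assessment sends the 4-week data to the coordinating centre on a CRF and mentions no SAE form.

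**The concern.** The word 'only' makes the 72-hour sentence exclusive. Read literally, it tells a site not to collect a serious event that starts on day 4 or later. The hold triggers, the death-reporting requirement and the SUSAR notification duty all assume that such events are collected. Two sites could therefore handle the same event differently, each following the protocol.

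There is also a practical gap. The trial deliberately asks about hospital stays weeks after vaccination, but does not say what happens when the answer is yes and the illness began after 72 hours. In a single-arm safety study, a serious event that the family has reported should have a defined place in the SAE system. Here its classification and speed of reporting depend on how a site reads two conflicting sentences.

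**Working it through.** The protocol gives no figure to reproduce. The check sets the provisions side by side and applies them to example events.

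**Which events are affected.** Under Definitions, a SAR is an adverse reaction that meets the seriousness criteria, and a SUSAR is a SAR that is unexpected. SUSARs are therefore a subset of SARs, and a limit on collecting SARs also limits SUSARs.

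**Example events.**

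1. A serious event starts on day 2 and the child dies on day 10. Onset is within 72 hours, so the event is collected and the provisions agree.
2. A serious event starts on day 10 and the child dies. The 72-hour sentence says not to collect it as an SAE. Item 1 of the SAE definition says to report the death, and Trial Closure makes it a hold trigger. The provisions conflict.
3. A suspected unexpected serious reaction starts on day 5 and the family mentions it in a call on day 6. The 72-hour sentence excludes it. Serious Adverse Event Reporting would have it notified, and Trial Closure would count it towards the SUSAR trigger. The provisions conflict.
4. A child with asthma falls ill on day 15, stays in hospital overnight, and the family says so at the 4-5 week contact. The stay can meet item 3 of the SAE definition. The 72-hour sentence excludes it from SAE collection, so it goes on the CRF, with no SAE form, no 24-hour report to the ISC and no onward report to the IDMC chair.

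**How much of the interval the window covers.** Inputs: a window of 72 hours = 3 days (Definitions); a contact at 4 to 5 weeks = 28 to 35 days (Appendix 3).

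- Contact at 4 weeks: 3 / 28 = 10.7% inside the window; 25 / 28 = 89.3% outside.
- Contact at 5 weeks: 3 / 35 = 8.6% inside; 32 / 35 = 91.4% outside.

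These are shares of calendar time. Turning them into shares of admissions would need the distribution of onset times, and a count would also need an admission rate and the number of children with asthma or recurrent wheeze. The protocol gives none of these.

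**The case against.** The strongest defence is that the short window is deliberate. It matches the primary outcome (2 hours), the delayed-reaction outcome (under 72 hours) and the first telephone call, in a pragmatic study of a licensed vaccine. Change in asthma control at 4 weeks has its own secondary outcome. The specific sentence on deaths can be read as an exception to the general limit, and the hold is triggered by the death itself rather than by an SAE form. The limit also applies to onset, so a late death from an early event is still collected.

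Much of this stands. A restricted SAE window can be legitimate, and a sensible site would probably report a death. But the protocol does not write the exception down, does not define the study period, and offers no comparable reading for SUSARs.

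The defence also rules out several stronger inferences that a reader might draw:

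- *Late events are lost to safety review or never reach the IDMC.* Not supported. All adverse events go on a CRF, the 4-week data go to the coordinating centre, and the IDMC reviews safety data after three months. What is missing is the SAE form and the expedited route.
- *Respiratory admission is the most plausible serious harm here.* Not supported. Background Information does cite "increased incidence of wheezing in children under 2 years old in the 4 weeks following immunisation", but such children cannot be enrolled. It adds that the effect is not seen in older children, including those with asthma or wheeze, and that post-marketing surveillance has not reproduced it.
- *About 89% of admissions would be missed.* Not supported. That figure is calendar time and becomes a share of admissions only if onset is spread evenly.
- *The online survey omits the hospital questions.* This cannot be judged, because the survey is not reproduced in the protocol.

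**Conclusion.** The conflict is real and can be seen in the text alone. As written, the 72-hour limit cannot be reconciled with the requirement to report every death, the two hold triggers quoted above or the study-wide notification of SUSARs. Separately, a hospital stay with onset after 72 hours, reported at 4-5 weeks by the family of a child with asthma or recurrent wheeze, can be an SAE by definition yet has no SAE route.

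The window covers 9-11% of the time that the hospital question spans. How many events are affected cannot be estimated from the protocol, and the number may be very small. The point does not depend on the count: a site that follows the limit literally would withhold the events on which the hold and SUSAR rules rely. That makes it more than a matter of missing detail. The conclusion assumes that 'only' means what it says and that no other study document supplies the exception.

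**What to change.** Reconcile Trial Closure, the asthma control assessment section, the Definitions and Serious Adverse Event Reporting sections, and Appendix 3. Three changes would do it:

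1. Amend the 72-hour sentence so that deaths and suspected SUSARs that the site learns of during the study period are expressly outside the limit.
2. Define the study period for an individual participant, so that the hold triggers and the reporting duties refer to the same interval.
3. State that any hospital stay reported at a scheduled contact (the 72-hour call, which may be as late as day 7, or the 4-5 week contact by either telephone or online survey) is assessed against the SAE criteria and, if it meets them, recorded on an SAE form.

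If the sponsor wishes to keep 72 hours for other serious events, it should say so and give the reason.

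The cost is a wording amendment, a few extra SAE forms, and an occasional call back to the family to complete one, for instance when the stay is reported online and causality and grade still have to be assigned. No new scheduled contact is needed.

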Allergic reactions to LAIV will be determined using the World Allergy Organisation (WAO) criteria for allergic reactions to immunotherapy, reproduced below. **For the purpose of this study**, mild symptoms of an allergic reaction (ie. non-anaphylactic symptoms) will be classified as non-serious adverse event, and should be documented on the CRF.

Any symptoms requiring treatment for anaphylaxis (adrenaline, steroids, salbutamol) **will be classified as a SERIOUS ADVERSE REACTION** and will be documented on both the CRF and a SAE form. The local investigator should also make a notification to the MHRA through the MHRA yellow card scheme.

On receipt of CRF / SAE forms, allergic reactions will be further classified by the ISC using World Allergy Organisation (WAO) criteria, which can be mapped to these grades and can be used to inform as to the appropriate NTI-CTCAE grade (Table 3).

Anaphylaxis will be defined as per the case definition and guidelines as described by the Brighton Collaboration Anaphylaxis Working Group (34) (see appendix 1).

WORLD ALLERGY ORGANISATION (WAO) GRADING SYSTEM FOR ALLERGIC REACTIONS TO IMMUNOTHERAPY

Grade 1	Grade 2	Grade 3	Grade 4	Grade 5

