
Symptom(s)/sign(s) of 1 organ system present*
 
Cutaneous Generalized pruritus, urticaria, flushing, or sensation of heat or warmth†
 
or
 
Angioedema (not laryngeal, tongue or uvular)
 
or
 
Upper respiratory Rhinitis - (eg, sneezing, rhinorrhea, nasal pruritus and/or nasal congestion)
 
or
 
Throat-clearing (itchy throat)
 
or
 
Cough perceived to originate in the upper airway, not the lung, larynx, or trachea
 
or
 
Conjunctival Erythema, pruritus or tearing
 
Other Nausea, metallic taste, or headache
	
Symptom(s)/sign(s) of more than 1 organ system present
 
or
 
Lower respiratory Asthma: cough, wheezing, shortness of breath (eg, less than 40% PEF or FEV₁ drop, responding to an inhaled bronchodilator)
 
or
 
Gastrointestinal Abdominal cramps, vomiting, or diarrhea
 
or
 
Other Uterine cramps
	
Lower respiratory Asthma (eg, 40% PEF or FEV₁ drop NOT responding to an inhaled bronchodilator)
 
or
 
Upper respiratory Laryngeal, uvula, or tongue edema with or without stridor
	
Lower or upper respiratory Respiratory failure with or without loss of consciousness
 
or
 
Cardiovascular Hypotension with or without loss of consciousness
	
Death

SERIOUS ADVERSE EVENT REPORTING

Serious adverse events and reactions must be reported to the PIs within 24 hours. An SAE/SUSAR form should be completed and faxed to the study coordination centre for all SAEs within 24 hours. This will then be communicated to the IDMC Chair, ISC chair and study sponsor. In the event of serious adverse reaction (expected), reporting should also include using the yellow card system.

In the case of suspected unexpected serious adverse reactions (SUSARS), the staff at the site should:

[figure not shown]
Complete the SAE case report form & send it immediately (within 24 hours, preferably by email or fax), signed and dated to the study coordination centre together with relevant treatment forms and anonymous copies of all relevant investigations.

Or

Contact the study coordination centre by phone and then send the completed SAE form to the study coordination centre within the following 24 hours as above.

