APPENDIX 1: BRIGHTON COLLABORATION CASE DEFINITION OF ANAPHYLAXIS³⁵

Anaphylaxis is a clinical syndrome characterized by:

- sudden onset AND
- rapid progression of signs and symptoms AND
- involving multiple (≥2) organ systems, as follows:

Level 1 of diagnostic certainty
 
 • ≥1 major cardiovascular AND/OR ≥1 major respiratory criterion AND • ≥1 major dermatological criterion

Level 2 of diagnostic certainty
 
 • ≥1 major cardiovascular AND ≥1 major respiratory criterion OR • ≥1 major cardiovascular OR respiratory criterion AND • ≥1 minor criterion involving ≥1 different system (other than cardiovascular or respiratory systems) OR • (≥1 major dermatologic) AND (≥1 minor cardiovascular AND/OR minor respiratory criterion)

Level 3 of diagnostic certainty
 
 • ≥1 minor cardiovascular OR respiratory criterion AND • ≥1 minor criterion from each of ≥2 different systems/categories

Note that all levels of diagnostic certainty **require the involvement the cardiovascular and/or respiratory systems.**

Organ System	Major Criteria	Minor Criteria
Skin or mucosal	
 • generalized urticaria (hives) or erythema • angioedema, localized or generalized • generalized pruritus with skin rash 	
 • generalized pruritus without skin rash • generalized prickle sensation • localized injection site urticaria • red and itchy eyes
Cardiovascular	
 • measured hypotension OR • shock (at least 3 of the following): 
 ▪ tachycardia ▪ capillary refill time (CRT) >3 sec ▪ reduced central pulse volume ▪ decreased level or loss of consciousness 	
 • Reduced peripheral circulation (at least 2 of: 
 • Tachycardia • CRT >3 sec without hypotension • Decreased level of consciousness
Respiratory	
 • Bilateral wheeze (bronchospasm) • Stridor • Swelling of upper airways • Respiratory distress (at least 2 of tachypnoea; use of accessory respiratory muscles; recession; cyanosis; grunting) 	
 • Persistent dry cough • Hoarse voice • Difficulty breathing without wheeze or stridor • Sensation of throat closure
Gastrointestinal		
 • Diarrhoea • Abdominal pain • Nausea • Vomiting

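### Equating mild with non-anaphylactic makes some allergic reactions non-serious under one rule and serious under another

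*Protocol*

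**What the plan says.** Three tests in the protocol bear on whether an allergic reaction is serious.

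- **Non-anaphylactic rule** (Grading and Attribution of Adverse Events: Allergic Reaction). A sentence marked as specific to this study states that "mild symptoms of an allergic reaction (ie. non-anaphylactic symptoms) will be classified as non-serious adverse event", to be recorded on the CRF. The section then adopts the Brighton Collaboration case definition of anaphylaxis. Appendix 1 describes a syndrome "involving multiple (≥2) organ systems, as follows", and notes that every level of certainty needs cardiovascular and/or respiratory involvement.
- **Drug-triggered rule** (Definitions, and again in the paragraph after the sentence above). It covers "Any symptoms requiring treatment for anaphylaxis (adrenaline, steroids, salbutamol"), and such a reaction "will be classified as a SERIOUS ADVERSE REACTION and must be documented on both the CRF as well as through completion of a SAE form".
- **General criteria** (Adverse Event Reporting, Definitions). Criterion 3 for an SAE is "Inpatient hospitalization or prolongation of existing hospitalization". For events attributed to the vaccine the section continues: "If the adverse reaction meets the above criteria (1-6) then it is termed a" serious adverse reaction. Allergic reactions are not excepted.

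The equation of mild with non-anaphylactic also appears in Treatment of Allergic Reactions: "mild (non-anaphylactic) symptoms should be treated with a long-acting, non-sedating oral antihistamine".

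**The concern.** The abbreviation *ie.* is definitional: it makes mild mean non-anaphylactic. Under the Brighton definition, though, a reaction can fall short of anaphylaxis because it involves one organ system, or because the systems involved are neither cardiovascular nor respiratory. Neither makes it mild, and neither keeps a child out of hospital. The protocol gives no order of precedence among the three tests, and a site could reasonably take a sentence marked as study-specific to override the general definition.

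What is at stake is reporting. An SAE goes on an SAE form to the coordination centre within 24 hours and from there to the IDMC chair, the ISC chair and the sponsor. A serious adverse reaction also goes to the MHRA by yellow card. A reaction taken as non-serious is entered on the CRF. Two sites could class the same admitted child differently.

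**Working it through.** **The plan's one design figure, to see whether it is touched.** Sample Size Estimation gives 730 children and an upper 95% limit of 0.5% if no event is seen. The exact two-sided limit for zero events is 1 − 0.025^(1/n). With n = 730 it is 0.504%, which reproduces the stated figure. The event there is a systemic or significant local allergic reaction, and the primary outcome is any immediate allergic reaction within 2 hours. Neither uses the serious label, so the limit is unaffected.

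**Case 1: generalised urticaria, angioedema (not of the airway) and vomiting; inpatient admission; no adrenaline, steroid or salbutamol required.** Against Appendix 1:

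- Level 1 needs a major cardiovascular or respiratory criterion. There is none.
- Level 2 needs a major cardiovascular or respiratory criterion, or a minor one alongside a major skin criterion. There is none.
- Level 3 needs a minor cardiovascular or respiratory criterion. There is none.

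The reaction is therefore not anaphylaxis.

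**Case 2: isolated wheeze, salbutamol required, no other organ system involved.** Bilateral wheeze is a major respiratory criterion, but each level also needs a second system. Again this is not anaphylaxis.

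| Test | Case 1 | Case 2 |
|---|---|---|
| Non-anaphylactic rule | non-serious | non-serious |
| Drug-triggered rule | not triggered | serious adverse reaction |
| SAE criteria in Definitions | serious (criterion 3, admission) | serious only if a listed criterion is met |

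In case 1 the study-specific sentence contradicts the general definition, and the drug rule does not settle it. In case 2 consecutive paragraphs of one section give opposite classes.

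**Timing.** The serious route requires a form within 24 hours. On the other route, Telephone Follow Up Visit has the CRF deemed complete and forwarded only after the family has been called, at least 72 hours and up to 7 days after vaccination. If the event occurs soon after vaccination, the coordination centre could learn of it about 2 to 6 days later (72 − 24 = 48 hours; 7 − 1 = 6 days). The ISC classifies reactions when the forms arrive, so its review cannot restore the 24-hour report.

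**The case against.** The strongest reply is that the sentence speaks of mild symptoms and does not claim to override Definitions. Those criteria carry no exception for allergy, and the reporting sections require an SAE form for every SAE. A careful site would report an admitted child as serious, and the protocol nowhere says that a non-anaphylactic reaction goes on the CRF *only*. This has force: the sentence need not be read as fixing every non-anaphylactic reaction as non-serious. But it defines its own term by *ie.* and is marked as study-specific, so the literal reading is open and nothing in the protocol closes it.

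Two stronger readings are tempting, and the documents do not support them.

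- *A reader might infer that any WAO grade 2 or 3 reaction short of the Brighton definition is wrongly called non-serious.* WAO grade measures severity and is not among the SAE criteria. A grade 2 reaction with vomiting, no admission, none of the three drugs and no other SAE criterion is non-serious under every rule. Grade 3 asthma is "Asthma (eg, 40% PEF or FEV₁ drop NOT responding to an inhaled bronchodilator"), which implies that a bronchodilator was tried. If salbutamol or steroids were required, the drug rule makes it serious. That rule catches most lower-airway reactions.
- *A reader might infer that missed serious reactions bias the safety estimate.* The exact upper limit for 730 children is 0.76% with one event and 0.99% with two, against 0.50% with none. These limits would describe a rate of serious reactions, which is not the stated outcome. All adverse events go on the CRF and the ISC grades allergic reactions, so both cases stay in the reaction count.

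It is also true that the hold triggers in Trial Closure are ventilation in intensive care, death and repeated SUSARs, not SAE counts, and that the IDMC's three-month review covers safety data recorded on the CRF. The practical effect is therefore limited to classification and prompt notification.

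**Conclusion.** The point stands as an unreconciled classification rule. The non-anaphylactic sentence, the drug-triggered rule and the SAE criteria give conflicting answers in two cases: an admitted non-Brighton reaction that required none of the three drugs, and a single-system reaction that required salbutamol. The effect is on the SAE/SAR label and count, the 24-hour report and notification of the IDMC chair, ISC chair and sponsor. There is no effect on the primary incidence or its 0.5% limit.

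The conclusion rests on two readings: that *ie.* is definitional, and, for case 2, that the drugs in brackets are themselves the trigger. If the drug rule applied only to drugs given for Brighton anaphylaxis, the case 2 conflict would disappear and case 1 would remain.

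No frequency can be given, and both cases are constructed illustrations. In the earlier study the documents report eight children with possible local symptoms, all mild and self-limiting, so few such events should be expected. Case 2 is plausible because children with asthma or recurrent wheeze are enrolled.

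**What to change.** Reconcile Definitions with the allergic-reaction section. Remove the bracketed equation of mild with non-anaphylactic from the classification sentence and replace the sentence with wording such as: *An allergic reaction is classified as non-serious, and documented on the CRF, only if it meets none of the SAE criteria in Definitions and does not trigger the adrenaline, steroid or salbutamol rule. This applies whether or not it meets the Brighton definition.* Carry the same wording into the CRF and SAE form guidance. Brighton level and WAO grade can still be reported as descriptors of the reaction.

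This concerns classification and reporting only. It proposes no change to how reactions are treated, and any change to the drug rule itself is for the sponsor and investigators. The cost is one sentence and its guidance text, possibly a few more SAE forms, and a slightly higher serious-event count.
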